10.5.1.2. Disallowed Concomitant Therapy

No other investigational drug may be used concomitantly with the study treatment.

The following concomitant medications are not permitted during the study:

- Acetylsalicylic acid doses >81 mg.
- Current systemic treatment with chemotherapy and/or other immunosuppressant drugs (unless advised otherwise after consult with the Medical Monitor)
- Any other FIX product (with exceptions listed in Section [11.1](#))

10.5.2. Concomitant Procedures

A concomitant procedure is any therapeutic intervention (e.g., surgery/biopsy, physical therapy) or diagnostic assessment (e.g., blood gas measurement, bacterial cultures) performed between the time the subject is enrolled in the study until the study is completed/terminated by the Sponsor, unless the subject is being followed for study-related toxicity.

CONFIDENTIAL

The information contained herein may not be used, disclosed, or published without the written consent of
Biogen Idec MA Inc.

The use of concomitant therapies or procedures defined above must be recorded on the subject's eCRF, according to instructions for eCRF completion. Adverse events (AEs) related to the administration of these therapies or procedures must be documented on the appropriate eCRF.

10.6. Continuation of Treatment

Subjects are expected to be followed through at least 100 exposure days (EDs) to rFIXFc and may further continue in this study for up to 4 years or until rFIXFc is commercially available in the applicable participating country.

CONFIDENTIAL

The information contained herein may not be used, disclosed, or published without the written consent of
Biogen Idec MA Inc.

11. WITHDRAWAL OF SUBJECTS FROM STUDY TREATMENT AND/OR THE STUDY

11.1. Discontinuation of Study Treatment

A subject *must* permanently discontinue rFIXFc for any of the following reasons:

- A Grade 2 or greater allergic drug reaction in association with administration of rFIXFc, as defined below by the Recommendations for Grading of Acute and Sub-Acute Toxic Effects on the World Health Organization (WHO) scale [[WHO handbook, 1979](#)]:
 - Grade 2 Bronchospasm related to rFIXFc; no parenteral therapy needed
 - Grade 3 Bronchospasm related to rFIXFc; parenteral therapy required
 - Grade 4 Anaphylaxis related to rFIXFc
- A high-titer inhibitor (≥ 5.00 BU/mL), as defined in Section 7.1.2.
- Use of FIX products other than rFIXFc, unless it occurs in one life-threatening emergency and/or as a result of one accidental use, and the Sponsor agrees to retain the subject in the study. Use must be recorded in the subject's eDiary and eCRF and the Investigator should contact the Sponsor Medical Monitor.
- Any condition a subject develops that precludes him from complying with the study procedures.
- The subject experiences a medical emergency that necessitates discontinuation of treatment.
- Clinical judgment of the Investigator: a subject may have treatment permanently discontinued if, in the opinion of the Investigator, it is not in the subject's best interest to continue with the study treatment.
- The parent or legal guardian can withdraw the subject from the study at will at any time.
- The subject and/or his parent/guardian withdraw consent.
- At the discretion of the Investigator or Sponsor for noncompliance.

The reason for discontinuation of study treatment must be recorded in the subject's eCRF.

CONFIDENTIAL

The information contained herein may not be used, disclosed, or published without the written consent of Biogen Idec MA Inc.

For any subject who no longer responds to treatment with rFIXFc, as determined by the Investigator, a decision will be made with the Sponsor whether to continue the subject on the study.

Subjects who discontinue treatment should remain in the study to complete protocol-required tests and assessments, and then must be permanently withdrawn from the study.

11.2. Withdrawal of Subjects From Study

Subjects must be withdrawn from the study for any one of the following reasons:

- The subject and/or parent/guardian withdraw consent.
- The subject and/or parent/guardian are unwilling or unable to comply with the protocol
- The subject meets any of the criteria defined in Section [11.1](#).

The reason for the subject's withdrawal from the study must be recorded in the subject's eCRF.

Subjects who discontinue study treatment and are withdrawn from the study will not be replaced.

If the decision is made to withdraw the subject from the study, the final study visit/early termination visit will be performed, as described in Section 4 ([Table 1](#)).

CONFIDENTIAL

The information contained herein may not be used, disclosed, or published without the written consent of
Biogen Idec MA Inc.

12. STUDY TREATMENT MANAGEMENT

Please refer to the Directions for Handling and Administration (DHA) for full details regarding rFIXFc.

The study treatment must be stored in a secure location. Accountability for study treatment is the responsibility of the Investigator. More details concerning this responsibility are included in Section 12.1.4. Study treatment must only be dispensed by designated study staff. Study treatment is to be dispensed only to subjects, to parents/legal guardians of subjects enrolled in this study, or to Sponsor-approved designees. Once study treatment is dispensed to a subject, it can only be administered to that subject. Study treatment vials are for one-time use only; any study treatment remaining in the vial should not be used for another subject.

Study site staff should refer to the DHA located in the Study Reference Manual for specific instructions on the handling, preparation, administration, and disposal of the study treatment. **The DHA supersedes all other references (e.g., Investigator's Brochure).**

The subject or the subject's caregiver must return to the investigational site for dispensation of rFIXFc and administration supplies before the earliest expiration date of drug in the subject's inventory. This is to ensure that adequate drug supplies for treatment are maintained, including an adequate supply to treat breakthrough bleeding or due to delays in scheduling clinic visits.

12.1. rFIXFc (BIIB029)

rFIXFc is supplied in a kit that contains several components: a vial of lyophilized drug, the diluent syringe, a filter device vial adapter, and a winged injection set. The lyophilized powder is in a clear glass vial containing 250, 500, 1000, 2000, or 3000 IU of rFIXFc (nominal strengths). Not all strengths may be available at the start of the study. The drug product is reconstituted with a diluent syringe containing 5 mL of [REDACTED] sodium chloride. After reconstitution of the lyophilized drug product, the concentrations of excipients for the 250, 500, 1000, and 2000 IU/vial strengths are [REDACTED] L-histidine, [REDACTED] sucrose, [REDACTED] mannitol, [REDACTED] polysorbate 20, and [REDACTED] sodium chloride. The concentrations of excipients for the 3000 IU/vial strength are [REDACTED] L-histidine, [REDACTED] sucrose, [REDACTED] mannitol, [REDACTED] polysorbate 20, and [REDACTED] sodium chloride.

The label will be compliant with local labeling requirements.

12.1.1. rFIXFc Preparation

The individual preparing rFIXFc should first carefully review the instructions provided in the DHA (if site staff), or in subject information materials provided by the site.

If the packaging is damaged, or if there is anything unusual about the appearance or attributes of the vials or drug, it should not be used. The vial in question should be saved by the subject or site, and then immediately reported by the site to the Sponsor.

CONFIDENTIAL

The information contained herein may not be used, disclosed, or published without the written consent of Biogen Idec MA Inc.

12.1.2. rFIXFc Storage

Site stocks of rFIXFc kits should be stored at 2°C to 8°C in a monitored, locked refrigerator with limited access or the room in which the refrigerator resides must be locked and have limited access.

12.1.3. rFIXFc Handling and Disposal

The Investigator must return all unused vials/kits of rFIXFc as instructed by the Sponsor. The instructions for return will be provided to the site at the time the request is made by the Sponsor.

If the Sponsor requires the study site to destroy unused rFIXFc kits, the institution/Principal Investigator(s) must notify the Sponsor, in writing, of the method of destruction, the date of destruction, and the location of destruction.

12.1.4. rFIXFc Accountability

The study site must maintain accurate records, demonstrating dates and amount of study treatment received, to whom dispensed (subject-by-subject accounting), amount returned by the subject, and accounts of any study treatment accidentally or deliberately destroyed.

The subject or the subject's caregiver should return all vials (used and unused) at each clinic visit for full medication exchange and accountability. At the end of the study, reconciliation must be made between the amount of rFIXFc supplied, dispensed, and subsequently returned to the Sponsor. A written explanation must be provided for any discrepancies.

CONFIDENTIAL

The information contained herein may not be used, disclosed, or published without the written consent of
Biogen Idec MA Inc.

13. EFFICACY ASSESSMENTS

Subjects that enroll into this study will be assessed only for those parameters that had been previously assessed in the parent study.

13.1. Clinical Efficacy Assessments

The following clinical tests/assessments will be performed to assess the efficacy of rFIXFc.

For all subjects:

- Number of bleeding episodes reported by each subject or the subject's caregiver during the study period
 - Recording of bleeding episodes in the hospital in the eCRF by the Surgeon/Investigator; recording of all other bleeding episodes in the eDiary by the subject or subject's caregiver
- Dose and dosing interval adjustments
- Assessment of response to treatment using a 4-point scale in the eDiary ([Appendix C](#))
 - Assessment of response to bleeding episodes using a 4-point scale by the Investigator for individual bleeding episodes treated in the clinic; assessment of all other bleeding episodes in the eDiary by the subject or subject's caregiver
- Physician's global assessment of response to the subject's treatment regimen using a 4-point scale ([Appendix D](#))

For subjects undergoing surgery, in addition to the above

- Investigator/Surgeon assessment of hemostatic response using the 4-point bleeding response scale ([Appendix E](#))
- Number of injections and dose per injection to maintain hemostasis during the surgical period
- Number of blood product units transfused during surgery
- Estimated blood loss (mL) during surgery and the post-operative period

Refer to Section [4](#) for the timing of assessments.

CONFIDENTIAL

The information contained herein may not be used, disclosed, or published without the written consent of Biogen Idec MA Inc.

13.2. Laboratory Efficacy Assessments

The following laboratory tests/assessments will be performed to assess the efficacy of rFIXFc:

- FIX activity, peak (recovery) and/or trough measurements, if applicable (determined by the one-stage aPTT clotting assay performed at the central laboratory)

Refer to Section 4 for the timing of assessments.

13.3. Pharmacokinetic Assessments

Not applicable.

13.4. Pharmacodynamic Assessments

Not applicable.

13.5. Additional Assessments

In addition to the efficacy assessments above, the following tests will be performed.

13.5.1. Hemophilia Joint Health Score

Joint assessment will be conducted at Visit 1 using a modified Hemophilia Joint Health Score (HJHS) for adult subjects. This assessment is based on the scoring system used in a joint scoring reliability study in boys with hemophilia [Hilliard 2006]. It has been used as a tool to evaluate musculoskeletal outcomes in a cohort of 20 boys, aged 4 to 17 years [Saulyte Trakeymiene 2010]. Modifications were included to adapt the HJHS scoring system to an adult hemophilia population and according to comments in a recent validation study by the International Hemophilia Prophylaxis Study Group [Feldman 2011].

Pediatric subjects will continue to use the HJHS, Version 2.1, and a joint assessment will be conducted at Visit 1. Version 2.1 was published as an appendix to a validation study of Version 1.0 [Feldman 2011].

Subjects from other parent studies will continue to use the joint health assessment instrument used in parent study.

Joint health assessments will only be performed if they were conducted during the parent study.

13.5.2. Patient-Reported and Health Outcomes

Only patient-reported outcomes that were completed during the parent study should be completed during the current study. If a subject goes outside of the age range for a questionnaire, he should no longer complete it. The following patient-reported outcome assessments will be performed, if applicable, for all subjects every 6 months, where linguistic validations exist in which the subject and/or parent/guardian is fluent. For pediatric subjects,

CONFIDENTIAL

The information contained herein may not be used, disclosed, or published without the written consent of Biogen Idec MA Inc.

caregivers will perform these assessments, as appropriate. The Investigator will administer the following age-appropriate questionnaires at the appropriate visits.

- Haem-A-QoL [[von Mackensen & Gringeri 2009](#)]
- Haemo-QoL [[von Mackensen 2004](#)]
- Hemo-Sat-Patient Satisfaction Scale for parent/guardian, Version 15 [[MAPI Research Institute 2009](#)]
- CHO-KLAT [[CHO-KLAT 2009](#)]
 - Children Version 2.0 (for children previously enrolled in study 9HB02PED who are less than 18 years of age).
 - Proxy, Version 2.0p (for parent/guardian of children who were previously enrolled in study 9HB02PED and who are less than 18 years of age)
- EQ-5D-Y [[EQ-5D-Y 2011](#)]
- EQ-5D-3L [[EuroQol 1990](#)]

Other patient-reported health outcomes related to hemophilia that are assessed include:

- Number of hospitalizations, excluding pre-planned hospitalizations, elective surgery documented at Visit 1, and emergent surgery
- Number of emergency room visits
- Number of physician visits excluding study visits
- Number of hospitalization days
- Number of days off work, school/daycare, or preschool
- Number of days off work for a parent/guardian

13.5.3. Optional Laboratory Assessment

For subjects who give their consent (or whose parent/guardian gives consent for pediatric subjects), a sample of blood will be collected during the study to conduct an analysis of genetic risk factors in the hemophilia B patient population. This exploratory laboratory assessment consists of DNA testing with full genome sequence.

CONFIDENTIAL

The information contained herein may not be used, disclosed, or published without the written consent of Biogen Idec MA Inc.

13.5.4. Archive Plasma Samples

Samples for FIX inhibitor testing will be collected for each subject, at each visit, for back-up and archiving. Samples will be archived for testing (if required) for immunology, further coagulation assays, or for clarification of any clinical or laboratory AE.

CONFIDENTIAL

The information contained herein may not be used, disclosed, or published without the written consent of
Biogen Idec MA Inc.

14. SAFETY ASSESSMENTS

Subjects that enroll into this study will be assessed only for those parameters that had been previously assessed in the parent study.

14.1. Clinical Safety Assessments

The following clinical assessments will be performed to assess the safety profile of rFIXFc:

- Physical examination
- Vital signs (blood pressure, pulse, respiratory rate, and temperature [°C])
- Medical and surgical history (from previous study and updated)
- Height
- Weight
- Concomitant therapy and procedures
- AEs and SAEs

Refer to Section 4 for the timing of assessments.

14.2. Laboratory Safety Assessments

The following laboratory tests will be performed by the central laboratory to assess the safety profile of rFIXFc:

- Hematology: White blood cell count (WBC), differential, platelet count, hemoglobin, hematocrit
- Blood chemistry: sodium, potassium, chloride, glucose, total protein, total bilirubin, alanine aminotransferase (ALT), aspartate aminotransferase (AST), alkaline phosphatase (ALP), blood urea nitrogen (BUN), and serum creatinine.
- Nijmegen-modified Bethesda assay for development of inhibitors
- Refer to Section 4 for the timing of assessments.

CONFIDENTIAL

The information contained herein may not be used, disclosed, or published without the written consent of Biogen Idec MA Inc.

15. SAFETY DEFINITIONS, MONITORING, AND REPORTING

Throughout the course of the study, every effort must be made to remain alert to possible AEs. If an AE occurs, the first concern should be for the safety of the subject. If necessary, appropriate medical intervention should be provided.

At the signing of the informed consent form (ICF), each subject must be given the names and telephone numbers of study site staff for reporting AEs and medical emergencies.

15.1. Definitions

15.1.1. Serious Pretreatment Event

The term “serious pretreatment event” is not applicable in this extension study as all AEs occurring up to the time of subject consent in this study will be captured as part of the subject’s previous study records.

15.1.2. Adverse Event

An AE is any untoward medical occurrence in a patient or clinical investigation subject who has been administered a pharmaceutical product and who does not necessarily have a causal relationship with this treatment. An AE can, therefore, be any unfavorable and unintended sign (including an abnormal laboratory finding), symptom, or disease temporally associated with the use of a medicinal (investigational) product, whether or not it is related to the medicinal (investigational) product.

Bleeds in this patient population are generally not considered AEs. Bleeding episodes that meet any criteria of “serious” (Section 15.1.3) should be reported as SAEs. All bleeding episodes will be captured in the eDiary maintained by the subject throughout the study period.

15.1.3. Serious Adverse Event

An SAE is any untoward medical occurrence that, at any dose:

- results in death
- in the view of the Investigator, places the subject at immediate risk of death (a life-threatening event); however, this does not include an event that, had it occurred in a more severe form, might have caused death
- requires inpatient hospitalization or prolongation of existing hospitalization
- results in persistent or significant disability/incapacity
- results in a congenital anomaly/birth defect

CONFIDENTIAL

The information contained herein may not be used, disclosed, or published without the written consent of Biogen Idec MA Inc.

All major surgeries will be reported as SAEs. An SAE may also be any other medically important event that, in the opinion of the Investigator, may jeopardize the subject or may require intervention to prevent one of the other outcomes listed in the definition above. (Examples of such medical events include allergic bronchospasm requiring intensive treatment in an emergency room or convulsions occurring at home that do not require an inpatient hospitalization).

15.2. Monitoring and Recording Events

15.2.1. Serious Pretreatment Events

A serious pretreatment event is not applicable in this extension study as all AEs occurring up to subject consent in this study will be captured as part of the subject's previous study records.

15.2.2. Adverse Events

Any AE experienced by the subject during participation in this extension study is to be recorded on the eCRF, regardless of the severity of the event or its relationship to the study treatment.

In addition, any known, untoward event that occurs subsequent to the AE reporting period that the Investigator assesses as related to the investigational medication/product should also be reported as an AE.

15.2.3. Serious Adverse Events

Any SAE experienced by the subject between the day of signing the ICF and the last study follow-up visit/telephone call is to be recorded on an SAE Form and eCRF, regardless of the severity of the event or its relationship to study treatment. Serious adverse events that occur up to 21 days after the subject's last dose of rFIXFc must also be recorded on the SAE Form and eCRF. Serious adverse events must be reported to Quintiles and to designated personnel, as detailed in the study file.

Any SAE that is ongoing when the subject completes the study or discontinues from the study will be followed by the Investigator until the event has resolved, stabilized, or returned to baseline status.

Subjects will be followed for all SAEs until the last study follow-up visit/telephone call. Thereafter, the event should only be recorded if the Investigator considers it related to study treatment.

In this study, the following events are considered medically important and must be reported as SAEs:

- A subject develops an inhibitor, as defined in Section [7.1.2](#).

CONFIDENTIAL

The information contained herein may not be used, disclosed, or published without the written consent of Biogen Idec MA Inc.

- A Grade 2 or greater allergic drug reaction in association with administration of rFIXFc, as defined below by the Recommendations for Grading of Acute and Sub-Acute Toxic Effects on the WHO scale [[WHO handbook 1979](#)]:
 - Grade 2 Bronchospasm related to rFIXFc; no parenteral therapy needed
 - Grade 3 Bronchospasm related to rFIXFc; parenteral therapy required
 - Grade 4 Anaphylaxis related to rFIXFc
- A subject develops a vascular thrombotic event in association with the administration of rFIXFc, with the exception of IV injection site thrombophlebitis.

All major surgeries will be reported as SAEs.

Subjects will be informed of early symptoms and signs of thrombotic phenomena, including pain and/or tenderness along a vein, swelling of an arm or leg without pain or tenderness, redness along a vein, low fever without any known reason (such as a cold or flu), sudden shortness of breath or difficulty breathing or coughing, sudden chest pain, sudden severe headache or changes in vision, and numbness or tingling in arms or legs. If such an event occurs while the subject is at home, the subject should be instructed to seek immediate medical care.

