13. Changes in patient-reported health outcomes assessed during the parent study are to be queried in the subject's electronic patient diary (eDiary) on an ongoing basis, and details are to be recorded in the electronic case report form (eCRF).

CONFIDENTIAL

The information contained herein may not be used, disclosed, or published without the written consent of Biogen Idec MA Inc.

14. Subjects entering the extension study from 998HB102 should continue to use the Modified Hemophilia Joint Health Score. Subjects entering the extension study from 9HB02PED should continue to use the HJHS Version 2.1. Subjects entering the extension study from other parent studies should continue to use the Joint Health Score instrument that is consistent with his parent study. Following Visit 7, the HJHS assessment will continue to be performed annually. The HJHS assessment is not required at the Final Study Visit if it was performed within the last 9 months.
15. Unscheduled visits may be necessary during the study, as determined by the Investigator, for reasons that may include repeating safety assessments, repeating blood sampling, testing FIX activity levels if required, or changing dose/regimen. For subjects from a parent study who undergo surgery and enter the extension study before completing their Last Post-Operative Visit, an unscheduled visit may be conducted to perform the Last Post-Operative Visit assessments when the subjects switch from their post-surgery dosing regimen to a regimen outlined in Section 5.3.2 (see Section 5.3.3 for list of assessments). Inhibitor testing will be performed at the time subjects reach 10 to 15 EDs, 50 to 75 EDs, and after 100 EDs, as applicable (The total ED is the combined rFIXFc exposure days from a previous rFIXFc study and this extension study). If the timing for inhibitor testing does not coincide with a scheduled visit, an unscheduled visit may be conducted.
16. A follow-up telephone visit is required 14 (+7) days after the last dose of study rFIXFc to monitor AEs, SAEs, and concomitant medications and therapies. This 14 (+7) day follow-up visit is not required if a subject ends his participation in the extension study to enroll into another rFIXFc study, however, a final visit/early termination visit is required.

CONFIDENTIAL

The information contained herein may not be used, disclosed, or published without the written consent of Biogen Idec MA Inc.

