7.2.3. Follow-Up

A final study visit will be conducted approximately 14 (+7) days after treatment with the last dose of study drug rFIXFc. This 14 day follow-up visit is not required if a subject ends his participation in the extension study to enroll into another rFIXFc study.

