15.2.5. Immediate Reporting of Serious Adverse Events

In order to adhere to all applicable laws and regulations for reporting an SAE, the study site must formally notify Quintiles Pharmacovigilance within 24 hours of the study site staff becoming aware of the SAE. It is the Investigator's responsibility to ensure that the SAE reporting information and procedures are used and followed appropriately.

CONFIDENTIAL

The information contained herein may not be used, disclosed, or published without the written consent of Biogen Idec MA Inc.

Reporting Information for SAEs

Any Serious Event that occurs between the time the subject has signed the ICF and up to 21 days after the final dose of study treatment must be reported to Quintiles Pharmacovigilance within 24 hours of the study site staff becoming aware of the event.

A report ***must be submitted*** to Quintiles Pharmacovigilance regardless of the following:

- whether or not the subject has undergone study-related procedures
- whether or not the subject has received study treatment
- the severity of the event
- the relationship of the event to study treatment

To report initial or follow-up information on a Serious Event, fax a completed SAE form to the following:

Fax: Please fax to Quintiles Pharmacovigilance at the country-specific fax number provided in the Study Manual.

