5.3.4. Safety Period

The safety period is defined as the period from 9HB01EXT Study Day 1 to the last recorded date. The end of the safety period will be imputed as 23:59 for the time on the last recorded date in the analysis database. The last recorded date is either the date of the last study visit, last telephone call, or the date of the last dose, whichever comes last.

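### Protocol 15.2.3 sets two conflicting end points for recording SAEs after the last dose, and a compliant day-14 contact leaves 7 of the 21 days with no scheduled contact

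*Protocol*

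**What the plan says.** Four places in the protocol bear on how long SAEs are collected after treatment ends.

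- **Section 15.2.3, 21-day rule.** After covering the time from consent to the last follow-up contact, the section adds a fixed limit: "Serious adverse events that occur up to 21 days after" the last dose must also be recorded on the SAE form and the eCRF.
- **Section 15.2.3, contact rule.** Later in the section, subjects are followed for all SAEs only up to the last follow-up visit or call. Then: "Thereafter, the event should only be recorded if the Investigator considers it related to study treatment".
- **Section 15.2.5.** Serious events from consent "up to 21 days after the final dose of study treatment must be reported to Quintiles Pharmacovigilance within 24 hours" of site awareness. The list of things that do not limit this duty includes "the relationship of the event to study treatment".
- **Timing of the contact.** Table 1, footnote 16: "A follow-up telephone visit is required 14 (+7) days after the last dose of study rFIXFc to monitor AEs, SAEs" and concomitant treatments. Section 7.2.3: "A final study visit will be conducted approximately 14 (+7) days after treatment with the last dose of study drug rFIXFc". Both waive the contact for a subject who moves into another rFIXFc study.

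In the SAP, Section 5.3.4 ends the safety period at the latest of three dates: "The last recorded date is either the date of the last study visit, last telephone call, or the date of the last dose". The general definition of a treatment-emergent AE in Section 8.2.2 stops at the last visit or the follow-up call. The next paragraph of 8.2.2 counts all AEs from Study Day 1 of this study and gives no upper limit.

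**The concern.** The 21-day rule and the contact rule agree only if the contact falls on day 21 or later. The permitted window opens on day 14, so a site that calls on the first permitted day has followed the schedule and then faces two instructions for the days that remain. One requires every SAE. The other asks only for those the investigator attributes to treatment. No further contact is scheduled that would bring an event in those days to light; the two-monthly calls in Section 7.1 and Table 1 belong to the treatment period.

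The primary objective is long-term safety. As written, whether a late SAE enters the database can depend on the day the site telephoned and on the investigator's causality judgement. Section 15.2.5 expressly sets that second filter aside.

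**Working it through.** The documents state no figure on this point, so there is none to reproduce. The check has two parts.

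**1. Days of the 21-day window with no scheduled contact**

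Inputs: window length W = 21 days (Sections 15.2.3 and 15.2.5); contact day d from 14 to 21 (Table 1 footnote 16; Section 7.2.3).

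Formula: days remaining = W − d; share = (W − d) / W.

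| Contact day d | Days remaining | Share of 21 days |
|---|---|---|
| 14 | 7 | 33.3% |
| 15 | 6 | 28.6% |
| 16 | 5 | 23.8% |
| 17 | 4 | 19.0% |
| 18 | 3 | 14.3% |
| 19 | 2 | 9.5% |
| 20 | 1 | 4.8% |
| 21 | 0 | 0% |

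If contacts were spread evenly over days 14 to 21, which is an assumption because the documents give no distribution, the mean would be (7+6+5+4+3+2+1+0)/8 = 3.5 days, and 3.5/21 = 16.7%.

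**2. One event under each rule**

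Take a subject contacted on day 14 who has an SAE on day 18 that the investigator judges unrelated.

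- 15.2.3, 21-day rule: 18 ≤ 21, so it must be recorded.
- 15.2.5: 18 ≤ 21 and causality is irrelevant, so it must be reported.
- 15.2.3, contact rule: 18 > 14 and the event is unrelated, so it should not be recorded.
- SAP 8.2.2, general definition: it began after the last contact, so it is not treatment-emergent.
- SAP 8.2.2, study-specific sentence: it began after Study Day 1, so it is treatment-emergent.
- SAP 8.2.6: if recorded, it is listed, because all SAEs are listed.

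If the same subject is contacted on day 21, the day-18 event precedes the contact and every rule gives the same answer. The conflict is therefore confined to the days between an early contact and day 21, and to events judged unrelated. Events judged related are recorded under either rule.

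**The case against.** The strongest reply is that the intended rule is already clear. The word also in the 21-day sentence makes that sentence an addition to the contact-based limit, so collection runs to the later of the two. Section 15.2.5 confirms this in mandatory terms, while the related-only sentence merely says should. This is persuasive about intent. It does not rescue the related-only sentence, which on that reading is wrong for every day between an early contact and day 21.

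A reader might go further than the documents allow in four ways.

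- **That up to a third of the window goes unobserved.** It does not. Section 15 has every subject given site telephone numbers for reporting AEs, and the duty in 15.2.5 starts when staff become aware of an event, however they learn of it. What is missing is a scheduled contact. The exposure is to events nobody volunteers and to unrelated events that a site leaves out under the contact rule.
- **That every subject followed by telephone is affected.** A contact on day 21 is compliant and leaves no gap.
- **That the SAP adopts the shorter limit.** The safety period of SAP 5.3.4 is applied only in Section 8.2, to place AEs with incomplete onset dates; nothing uses it to drop events. The study-specific sentence in 8.2.2 has no upper limit, and 8.2.6 lists all SAEs. Only the general definition in 8.2.2 stops early, so the SAP is unclear rather than restrictive.
- **That residual factor activity between days 14 and 21 makes the gap riskier.** No passage links residual activity to the risk of SAEs after treatment, and the conflict does not depend on it.

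It is also fair to say that the period is short. Seven days against a maximum of 4 years in the study is 7/(4 × 365.25) = 0.5%. The primary endpoint, inhibitor development, rests on confirmed central laboratory results and is not touched by this conflict.

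**Conclusion.** Section 15.2.3 contradicts itself and Section 15.2.5, and one sentence is wrong as written. For a subject contacted before day 21, an unrelated SAE between the contact and day 21 falls under incompatible instructions, and no scheduled contact covers those days. The size is 0 to 7 of 21 days (0% to 33%), depending on the contact day; the 17% average holds only if contacts are evenly spread.

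The documents do not allow an estimate of how many SAEs would be missed. The range applies to subjects who have the 14 (+7) day contact. Those who move to another rFIXFc study need none, and the documents do not say whether the next study covers their remaining days. The point merits correction because it bears on SAE capture under a safety objective and is cheap to put right. It does not put the primary endpoint in doubt.

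**What to change.** **Protocol 15.2.3.** Replace the opening word of the related-only sentence with: After the later of 21 days post last dose and the last follow-up contact. The rest of the sentence can stand, and it then agrees with 15.2.5.

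**Table 1 footnote 16 and Section 7.2.3.** Set the follow-up contact no earlier than day 21 after the last dose. The two places also differ on whether it is a telephone call or a final visit; settle that in the same edit.

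**SAP 8.2.2.** End the general definition of a treatment-emergent AE at the later of the last contact and 21 days after the last dose, so that it no longer cuts off events the protocol requires.

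No change is needed to SAP 5.3.4, which does not exclude events, or to the concomitant-therapy window in protocol 10.5.1, where this review point identifies no problem.

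The cost is a few lines in one amendment and in the SAP. If the present 7-day allowance is kept, the latest contact moves from day 21 to day 28 (21 + 7), so the last subject closes up to about a week later.
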